We will systematically approach the challenge associated with the quantitative neurobiological study of co-addiction. We thoroughly characterize four subject groups demographically, clinically, cognitively and neurally. In order to construct the model, we will integrate several readily quantifiable aspects of brain function in individuals addicted to either alcohol, nicotine, both or neither. **SA1** uses the capabilities of the Advanced Imaging Research Center (AIRC) at Oregon Health & Science University (OHSU, VAPORHCS affiliated university) to obtain measures of task based neural activation, functional and anatomical connectivity and cortical density. Our preliminary data demonstrate that we can use functional and anatomical neuroimaging to differentiate groups who primarily use either nicotine or alcohol from both each other and from non-addicted control subjects (CS). Importantly, **Preliminary Study 1** demonstrates that neural response on a Probability/Delay Discounting task (PDD) differentiates individuals who remain abstinent after initial sobriety from alcohol and those who do not. **SA2** will use the data generated by **SA1** to develop the predictive multidimensional neural model and leverage our understanding of the cerebral basis of AUD and NUD to differentiate co-addicted vs. singly addicted individuals and to use neurobiological markers to predict success during early recovery.

SA 1: Test a dual network model of alcohol and nicotine co-addiction via contrast of multiple neural aspects of AUD, NUD, NAUD and CS: a) task based (PDD) and stress modulated cue induced craving, b) volumetric estimates of cortical density (voxel-based morphometry [VBM]), c) anatomical (diffusion tensor imaging [DTI]) and d) resting state functional connectivity.

Hypothesis 1a.1: **We hypothesize** that individuals co-addicted to alcohol and nicotine will exhibit a pattern of cortical activation to delay, magnitude and probability characterized by both increased sensitivity to reward in striatum and aversion to risk and delay in dorsal cognitive control regions. **(1a.2) Furthermore**, differences in neural activity between stressed and unstressed drug associated stimuli (DAS) will identify regions associated with cognitive control of DAS. We predict that parametric variation in cortical structures hypothesized to control response to DAS, will show greater stress-induced variation when the DAS represent the preferred substance.

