C3d. DSNBACK Analysis: This task is designed to identify brain regions in both the salience network that responds to drug cues and the executive network that suppresses responding to cues in order to attend to other tasks. For each subject a voxelwise linear mixed effects analysis (3dLME) with main effects of difficulty, stimulus class and a difficulty X stimulus interaction term will be calculated. The analysis of the scanner task will calculate parametric regressors (0 or 2-back) for each stimulus class (nicotine, alcohol and neutral). Contrasts between the drug and neutral stimuli during the 0 back condition will identify salience attribution regions, while the same contrasts during the 2-back will identify cognitive control regions.

Hypothesis 1a.2: Differences in neural activity between stressed and unstressed drug-associated stimuli (DAS) will identify regions associated with cognitive control of DAS. We predict that parametric variation in cortical structures hypothesized to control response to DAS, will show greater stress-induced variation when the DAS represent the preferred substance.

Expected Outcomes and Alternatives: We predict that addicted individuals will show a significant interaction between difficulty and drug condition. Specifically, we hypothesize that activation in ACC, PPC and DLPFC will show greater parametric scaling with stress when the subject suppresses drug cue distractors. More speculatively, we hypothesize that within individuals, preference for the drugs can be characterized by differences in neural response, difficulty and drug condition. Thus, we predict that the co-addicted group will show stress-induced parametric modulation with both nicotine and alcohol stimuli, although individual subjects may exhibit a preference for one substance. For example, although NUD subjects may use alcohol, they are predicted to have a more robust response to smoking cues. We will also correlate the ability to suppress drug stimuli to the volumetric and connectivity measures obtained in **SA1**. Secondarily, we expect cortical thinning in rostral ACC, PPC and DLPFC, as well as increased FA in white matter connections between these regions to correlate with inability to suppress drug stimuli and perform the task.

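### Hypothesis 1a.2 predicts a larger load effect for the preferred substance, but no test named in C3d isolates preferred from other drug by load

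*Combined protocol and SAP*

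**What the plan says.** Hypothesis 1a.2 appears in the Specific Aims and again in C3d. It predicts that the cortical structures thought to control responses to drug cues "will show greater stress-induced variation when the DAS represent the preferred substance". The comparator is not written out. The natural reading is the other drug, and the C3d paragraph on expected outcomes supports it: "although NUD subjects may use alcohol, they are predicted to have a more robust response to smoking cues".

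The C3d analysis has three stated parts:

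- A voxelwise mixed model in which "main effects of difficulty, stimulus class and a difficulty X stimulus interaction term will be calculated". Stimulus class has three levels: nicotine, alcohol and neutral.
- A contrast at low load: "Contrasts between the drug and neutral stimuli during the 0 back condition will identify salience attribution regions".
- A contrast at high load: "while the same contrasts during the 2-back will identify cognitive control regions".

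The general expected result is "We predict that addicted individuals will show a significant interaction between difficulty and drug condition". C3d also offers, as more speculative, that "within individuals, preference for the drugs can be characterized by differences in neural response, difficulty and drug condition", with no test attached. For the co-addicted (NAUD) group it expects modulation by both kinds of cue.

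C3d contains no preferred-versus-other contrast, no definition of the preferred substance, and no criterion for when 1a.2 is supported. C3b collects craving ratings separately for alcohol and nicotine, but C3d does not use them for this purpose.

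**The concern.** A claim about the preferred substance compares one drug with the other. The named contrasts compare drugs with neutral pictures, and the overall interaction asks only whether the load effect differs somewhere among three classes. A subject who reacts equally to alcohol and nicotine cues, and more to either than to neutral, can produce a significant result on each of them. The within-load contrasts also do not test a load effect at all; in C3d only the interaction does.

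At stake is the substance-specific part of 1a.2. Without a named test, general drug-cue reactivity could be reported as preference for a subject's own substance. The choice of a drug-versus-drug comparison, and its direction, would also be left until after the data are seen.

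**Working it through.** The plan gives no DSNBACK sample-size, effect-size or alpha figure to reproduce, so the check compares the contrasts directly and then illustrates the result.

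**Inputs.** From the documents: two load levels, three stimulus classes, 50 subjects per group (C8). Assumed: stress means 2-back versus 0-back; each subject's load effect (2-back minus 0-back) has SD 1 in each class with independent errors; a single test at two-sided 0.05; effects of d = 0.4, 0.5, 0.6 and 0.8 SD.

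**Step 1: what each test measures.** Order the load effects as (preferred, other, neutral).

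- Preference: (1, −1, 0).
- Pooled drug minus neutral: (½, ½, −1). Its product with the preference contrast is ½ − ½ + 0 = 0, so it carries no information on preference. The same weights applied within one load level have the same property.
- One drug minus neutral: (1, 0, −1) or (0, 1, −1). Under equal reactivity both have mean d. Only their difference, (1, −1, 0), concerns preference, and C3d does not name it.
- Overall interaction: 2 degrees of freedom, with noncentrality λ = n Σ(μ − mean μ)² / SD².

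**Step 2: the overall interaction under two patterns.**

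- Equal reactivity, μ = (d, d, 0), mean 2d/3: the sum of squares is 2(d/3)² + (2d/3)² = (2/3)d².
- Preferred drug only, μ = (d, 0, 0), mean d/3: the sum is (2d/3)² + 2(d/3)² = (2/3)d².

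The two are identical. At d = 0.5, λ = 50 × (2/3) × 0.25 = 8.33 in both. Under these assumptions the overall test has the same power for either pattern and cannot distinguish them.

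**Step 3: t tests at d = 0.5.**

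- Pooled drug minus neutral has variance ¼ + ¼ + 1 = 1.5. Under equal reactivity the noncentrality is 0.5 × √(50/1.5) = 2.89. Under a preferred-only effect the mean halves to 0.25 and the noncentrality is 1.44.
- Preferred minus other has variance 2. Under equal reactivity the noncentrality is 0. Under a preferred-only effect it is 0.5 × √(50/2) = 2.50.

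**Step 4: simulated rejection rates** (20,000 runs, n = 50, all on the load effect).

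| Test | Pattern | d = 0.4 | 0.5 | 0.6 | 0.8 |
|---|---|---|---|---|---|
| Pooled drug minus neutral | equal | 62% | 81% | 92% | 99% |
| Pooled drug minus neutral | preferred only | 20% | 30% | 40% | 61% |
| Overall interaction | equal | 52% | 73% | 87% | 99% |
| Overall interaction | preferred only | 52% | 72% | 87% | 99% |
| Preferred minus other | equal | 5% | 5% | 5% | 5% |
| Preferred minus other | preferred only | 50% | 69% | 84% | 98% |

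The pooled contrast is more often significant when there is no preference than when only the preferred drug acts. The preference contrast alone separates the patterns.

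**Step 5: coding matters.** With AUD and NUD combined and opposite preferences at d = 0.5, alcohol minus nicotine without preference coding cancels and rejects in about 4% of runs. The preference-coded version rejects in about 94%.

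**The case against.** Several points on the other side are sound.

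- **The model already contains the comparison.** One of the interaction's two degrees of freedom is nicotine versus alcohol by load. A reader might infer from the named contrasts that C3d compares drug cues only with neutral ones. That is true of those contrasts but not of the model. What is missing is a named, directional, preference-coded test.
- **No rule says equal reactivity would count as support.** A reader might infer this from the predicted interaction, but C3d states no decision rule for 1a.2. For that reason the rates above cannot be called false-positive rates for the preference claim. Those for drug minus neutral and the interaction under equal reactivity are power to detect a real drug-cue effect. The defensible statement is that a significant result could be misread.
- **NAUD is different.** Modulation by both drugs is the stated expectation there, so similar reactivity is not an anomaly. The gap is clearest in AUD and NUD.
- **Within-person preference is labelled speculative.** That label stands on its own sentence. It does not qualify the preferred-substance prediction written into 1a.2.
- **The figures are not calibrated to this task.** C3d is voxelwise and its named contrasts are taken within load, whereas the table uses one test on the load effect. The C8 calculations rest on a reward-magnitude map comparing AUD with CS, so no DSNBACK effect size can be taken from them.
- **The data are not lost.** Every condition is acquired, and the contrast could still be computed later. It would then be chosen after the fact.

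These points narrow the concern but do not supply the missing test.

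**Conclusion.** The point holds as a gap between hypothesis and test. C3d names drug-versus-neutral contrasts within each load level and an overall interaction. Neither isolates preferred from other drug by load, and each can be significant under equal reactivity. This rests on the algebra of the contrasts and on reading the unstated comparator as the other drug, which the NUD prediction supports.

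Its size can only be illustrated. With 50 subjects and assumed effects of 0.4 to 0.8 SD, the overall interaction rejects at practically the same rate under both patterns (about 52% to 99%). The preference contrast moves from about 5% to between 50% and 98%. Unequal variances or correlated errors would change these rates.

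The documents do not support the stronger conclusions that the comparison cannot be made from this design, or that the plan would declare preference shown when both drugs act alike. The plan should be amended: the tests it states cannot support a prediction it makes in a numbered hypothesis, and the remedy is cheap.

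**What to change.** In C3d:

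1. Name the test of the preferred-substance prediction as (2-back minus 0-back) × (preferred minus other drug) in ACC, PPC and DLPFC, with the direction stated.
2. Define preference by diagnosis in AUD (alcohol) and NUD (nicotine). In NAUD, use the difference between the alcohol and nicotine craving VAS scores. Craving is rated at several times, so specify the pre-task rating.
3. Report AUD and NUD separately, and also the crossed contrast: the nicotine-minus-alcohol load effect in NUD minus the same quantity in AUD. The crossed form removes average picture-set differences common to both groups. It still carries differences in abstinence status (Table 1 has AUD subjects alcohol-free for 2 to 8 weeks and NUD subjects currently smoking) and in the images each subject selects (C3b). Say so when interpreting it.
4. State that drug-versus-neutral contrasts and the overall interaction show general cue reactivity only and are not evidence of preference.

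The cost is wording and added contrasts on data already planned. The downside is precision: under the assumptions above, preferred minus other within a group has a standard error √(2/1.5) = 1.15 times that of pooled drug minus neutral, so the preference claim will be harder to reach.

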C3a. Probability Delay Discounting Task: Data from discounting tasks will be fit to equations in **Figure 2**. Standard temporal and probability discounting data will be fit (Eq. 1.1) using a softmax procedure (Miedl et al., 2012). The constants, k and h , are adjustable parameters that characterize the discounting rates (Bickel and Marsch, 2001). For standard discounting, $M = \$100$. As k and h are not normally distributed, we calculate the fractional areas under the discounting curves as impulsivity measures. We will use the formulation of Ho et al. (1999) for the PDD which posits the actual value of a delayed and probabilistically discounted reward, M , as Eq 1.2. The second function is that of the indifference surface with the immediate certain reward set at \$20. As the integral of the discounting function is separable, we calculate the volume under the surface as the product of a temporal and probability discounting function (Eq. 1.3), where the fractional areas A'_k and A'_h are equivalent to the areas under the curves for standard delay and probability discounting.

C3b. DSNBACK Task: Before the task, subjects will be evaluated for their level of craving for alcohol and nicotine by filling out a Visual Analog Scale (VAS) for each substance. Participants are shown two sets of images, each containing 36 nicotine or alcohol related stimuli. From the larger sets, they select the 6 alcohol images and 6 nicotine images that they consider most salient. Another VAS will be administered to determine if viewing the stimulus images caused increases in craving. Subjects then complete a familiarization task. At their next study visit, the participants will perform the DSNBACK in the MRI scanner. 0-back and 2-back blocks are administered in a randomized order with stimulus images shown to each side of the letter. Correct or incorrect responses and reaction times will be recorded for each letter in each trial. Subjects will rate craving for each drug before and after the scan.

C3b2. Follow Up Visits: During 3 monthly follow up visits, subjects will turn in journals which will document any lapse or relapse episodes, craving for nicotine and alcohol, treatment status, and use of nicotine, alcohol, drugs or medications. They will also undergo a short cognitive battery which repeats measures taken during the initial visits. All subjects will keep study journals throughout their participation in the study.

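### C3d and Hypothesis 1a.2: both rules for identifying cognitive control regions in the DSNBACK are confounded, one with the cue response and the other with working-memory load; the fitted interaction should define these regions

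*Combined protocol and SAP*

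**What the plan says.** The task description in C3b crosses two difficulty levels with flanking images: "0-back and 2-back blocks are administered in a randomized order with stimulus images shown to each side of the letter". The C3d analysis has "parametric regressors (0 or 2-back) for each stimulus class (nicotine, alcohol and neutral") and a mixed model in which "main effects of difficulty, stimulus class and a difficulty X stimulus interaction term will be calculated".

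Two sentences then state how control regions will be found.

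- **Rule A (C3d).** The drug-minus-neutral contrast at 0-back is reserved for salience regions. For the harder condition the plan relabels it, "while the same contrasts during the 2-back will identify cognitive control regions".
- **Rule B (Hypothesis 1a.2).** "Differences in neural activity between stressed and unstressed drug-associated stimuli (DAS) will identify regions associated with cognitive control of DAS". No neutral images enter this comparison.

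Under Expected Outcomes in the same section, the plan predicts the interaction itself: "We predict that addicted individuals will show a significant interaction between difficulty and drug condition". It also names regions in advance: "activation in ACC, PPC and DLPFC will show greater parametric scaling with stress when the subject suppresses drug cue distractors".

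**The concern.** C3d presents the task as a way to tell regions that respond to drug cues from regions that suppress that response. The label given to a region therefore has to depend on something that differs between the two processes.

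Under Rule A, a region that simply responds to drug images, equally at both difficulty levels, qualifies as salience at 0-back and again as control at 2-back. Under Rule B, a region that works harder at 2-back qualifies whatever image flanks the letter, and it could do so in control subjects as well. The two rules also differ from each other, so one region can be a control region under one and not under the other. An analyst who follows the text could report pure salience or pure load regions as regions that control drug cues.

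**Working it through.** **Inputs.** The design, stimulus classes and model terms come from C3b and C3d, and the 50 subjects per group from C8. The plan states no figure on this point, so there is none to reproduce. Effect sizes and the significance level below are assumptions. Reading stressed as 2-back is an inference: C3d uses stress and difficulty interchangeably but never equates them.

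**Step 1: cell means.** For one drug class against neutral, let B be the mean for neutral images at 0-back, S the drug-cue response at 0-back, L the load effect (2-back minus 0-back) with neutral images, and I the extra response to drug images at 2-back.

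| | 0-back | 2-back |
|---|---|---|
| Neutral | B | B + L |
| Drug | B + S | B + S + L + I |

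**Step 2: what each contrast estimates.**

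- Drug minus neutral at 0-back (salience rule): (B + S) − B = S
- Drug minus neutral at 2-back (Rule A): (B + S + L + I) − (B + L) = S + I
- Drug at 2-back minus drug at 0-back (Rule B): (B + S + L + I) − (B + S) = L + I
- Difficulty by stimulus interaction: (S + I) − S = I

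**Step 3: no load-dependent cue effect (I = 0).** Rule A reduces to S, the quantity that defines salience. Rule B reduces to L, the ordinary load effect. A region with S > 0 and L = I = 0 passes A and fails B. A region with L > 0 and S = I = 0 does the reverse. The interaction is zero in both.

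**Step 4: illustration of size.** Take n = 50 in one group, a one-sample t test, two-sided alpha 0.001 and I = 0. Let d be the nuisance effect (S for Rule A, L for Rule B) divided by the SD of the within-subject contrast. The probability that the simple contrast is significant follows from the noncentral t distribution with 49 degrees of freedom and noncentrality d√50.

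| Assumed d | Probability of a false control label |
|---|---|
| 0.3 | 0.10 |
| 0.5 | 0.52 |
| 0.6 | 0.763 |
| 0.8 | 0.980 |
| 1.0 | 1.000 |

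A two-sided test of the interaction would be significant at its nominal rate, 0.001, because its true value is zero by assumption.

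**Step 5: how much of Rule B is load.** The load share is L/(L + I). With assumed L from 0.1 to 2 and I of 0.25 or 0.5 on the same scale, it runs from 0.1/0.6 = 17% to 2/2.25 = 89%. It is 100% when I = 0.

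**Step 6: precision of the interaction.** With independent cells of equal variance σ², a simple contrast of two cells has variance 2σ² and the interaction, using four cells, has 4σ². The ratio is 2, so about twice as many subjects are needed to detect the same raw effect with the same power. No required number can be given, because the documents contain no DSNBACK effect size or SD.

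**The case against.** The strongest reply is that the plan already holds the right test. The interaction is in the model, Expected Outcomes predicts it and names ACC, PPC and DLPFC for it, and alcohol and nicotine already have separate regressors. The second sentence of Hypothesis 1a.2 compares stress-induced change between preferred and other cues, so a load effect common to both cancels. All of this stands. A reader might infer that the plan has no test of load-dependent cue processing, and that would be wrong. The fault lies in the two identification sentences, which do not refer to the interaction.

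A reader might also infer that Rule B measures mostly working-memory load. The documents give neither L nor I, and step 5 shows that the share could be small or large. Only confounding with load is supported.

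Third, a reader might infer that the dual-network comparison, or the classifier in C6, depends on these labels. Table 3 assigns salience and executive labels in advance. C6 lets the region set be adjusted after preliminary analysis, but according to measures that separate the four groups. Nothing says that the C3d labels feed the classifier.

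Finally, the interaction is not proof of suppression. A salience region whose cue response falls under load has I < 0, so a non-zero interaction without a stated direction would mislabel it too. This is correct, and the fix allows for it.

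**Conclusion.** Wrong as written, and should be fixed; it is not severe enough to invalidate the aim. The algebra needs no effect-size assumption: Rule A estimates S + I, Rule B estimates L + I, and only the interaction estimates I. The conclusion on Rule B rests on reading stressed as 2-back.

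The percentages in step 4 illustrate the mechanism. They depend on the assumed effect sizes, alpha and zero interaction, and are not estimates for this study. The consequence is limited to which regions are reported as controlling drug cues. The predicted interaction test is unaffected.

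**What to change.** In C3d and in the first sentence of Hypothesis 1a.2:

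- Define drug-cue control regions by a positive difficulty by stimulus interaction, (drug − neutral at 2-back) − (drug − neutral at 0-back), separately for alcohol and nicotine cues.
- Keep drug minus neutral at 0-back as the salience rule.
- Report drug minus neutral at 2-back, and drug cues at 2-back minus 0-back, as descriptive only.
- State that stressed means 2-back, if that is intended.
- Interpret a positive interaction as suppression only alongside the accuracy and reaction times that C3b already records.

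The cost is a few sentences of text, with no new data and no new model term. The statistical price is precision: about twice the variance of a simple contrast under equal, independent cell variances, so fewer regions may reach significance. The power estimate in C8 comes from a magnitude map comparing AUD and control subjects and is not described as covering this interaction. The plan should not cite it as assurance on this point.
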